certification and an accompanying performance fidelity monitoring process. This phase will occupy the project's first 14 months and will involve no human subject research participation. Phases 2 and 3 of the study involve human subject research participation. All human subject research activities will be conducted by members of the Emory study team, identified above; no non-Emory study team members will have any contact with Phase 2 and 3 research subjects. The second project phase, which will begin in project month 9 and extend through project month 24, will involve a formative evaluation of the prototype web-based system. In this phase, administrators and interventionists-in-training from 3 collaborating organizations and 36 informal dementia caregivers from these organizations will participate as research subjects. The administrators and interventionists will take part in semi-structured evaluation interviews; the caregivers will be asked to participate in Savvy programs offered by the newly-trained interventionists and they (the caregivers) will be asked to complete pre- and post-Savvy participation interviews both about the effect of the program on them and about their evaluation of the program. Phase 2 results will enable us to revise the interventionist training system, as needed. Once the system is deemed ready, we will, in phase 3, conduct a field test of the system implemented in six culturally and/or organizationally diverse sponsoring agencies. This test will again involve administrators, interventionists-in-training, and 120 dementia caregivers from participating organizations as research participants. The Aim 3 test will principally assess the effectiveness of the system in training interventionists who maintain fidelity to Savvy core principles; this portion of the test involves semi-structured interviews with the administrators, interventionists and a sample of caregivers. The test will also assess the preliminary efficacy of programs led by system-trained interventionists in producing anticipated outcomes in caregiver participants – reduced depression and burden and enhanced caregiving mastery. In this portion of the test, caregivers will be randomly chosen to participate immediately in a Savvy program offered by one of the organization's newly trained interventionists or to participate after a waiting period of 4 months. Those who

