## **Field Methods**

**Data Collection and Management.** Emory study staff will use an IRB-approved phone or video consent process to enroll individuals from the three groups that are targets for our formative evaluation activities, and study staff and team members will gather data from them in the ways described below:

*Interventionists.* We will conduct three recorded semi-structured video interviews with each interventionist. One will occur immediately after training; this will focus on their sense of the completeness and adequacy of the training program, including the training methods, videos, and materials, and their perceived readiness to lead the program. We will also interview them immediately after the conduct of each of the two Savvy programs they lead, asking them to report on their own performance as interventionists, including any adaptation processes in which they might have engaged, and to reflect on ways the training might be improved to strengthen their skills, including for adaptation. In total: 18 interviews.

*Savvy Participants.* Using an on-line survey method, we will ask each caregiver to complete the post-program fidelity monitoring survey (see Appendix) that seeks responses to the program (feel more knowledgeable, more competent, better equipped, etc.) and asks them to assess the interventionist's performance and verify that certain key elements of the program were covered (N=36; 6 in 6 groups). We will also conduct recorded semi-structured video interviews with a small sample of participants (N=8-12), selected to achieve maximum variability of relationship to care recipients, gender, racial/ethnic heritage, and rating of the program and the interventionists. Interviews will focus on caregivers' perceptions of the interventionist's

program leadership skills, any adaptation experiences, and on ways in which they met their own needs and expectations.

*Organizational Leaders.* We will conduct recorded semi-structured video interviews with sponsoring organizations' key contact persons immediately after the interventionist training and then after each of two Savvy offerings. The conversation will focus on identifying ways to strengthen and improve the training, certification, and fidelity monitoring system. We will also seek information about time and resource costs of the program, caregiver demand, and caregiver recruitment and feedback (3 interviews per organization).

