## **10. Plans for analysis**

Multi-level mixed effects models (MLM) with random (participant) and fixed (cohort) effects will be employed to test for linear (and non-linear) trajectories of change for the Intervention group versus waitlist

group focusing on the group-by-time effect. To address the primary effect of the Savvy intervention, the Immediate group will be compared to the waitlist delay group, using the first 2 time points (0m-2m) to test for differences between the 2 groups' changes post intervention. Additionally, the combined Savvy intervention effects will be assessed using a paired t-test for the combined immediate group's first 2 time points (0m-2m) with the waitlist delay group's 2 time points before and after beginning Savvy (4m-6m). If there are significant differences between the 2 groups at the time point immediately prior to receipt of the intervention, these "baseline" effects will be included and adjusted for a final analysis of covariance (ANCOVA) model for these change scores. Given that the immediate group will have 3 post-intervention measurements (2m-4m-6m), MLM longitudinal models will also be employed to assess the overall time effects plus planned post hoc comparisons for both the immediate intervention effect and the longer term and sustained effects. Sidak Type-I error rate adjustment (which has higher power than Bonferroni) will be applied for the multiple pairwise time point comparisons. The proposed study design also has the advantage of capturing "baseline" time points for the delay group (0m-2m-4m) which will provide an excellent opportunity to evaluate what if any potential "placebo" effects there may be from being enrolled in this type of study. These initial data captured at 0m-2m-4m for the delay group will also be used to evaluate any potential decline occurring during this time period. All model assumptions will be tested; grand mean centering used to help combat multi-collinearity between variables; and standard diagnostic tests and influence statistics used to test the distributions of the residuals. MLM models utilize all available data for all participants at each time point and have the advantage of adjusting for the missing data over time, where repeated measures ANOVAs do not. Further covariate predictors of missingness (mainly due to attrition) over time will be included to additionally adjust for these confounders SPSS v.24 will be used for all analyses at the 5% significance level.

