We will use a meta inference process to answer the central question of this project: Can the system train interventionists to maintain fidelity to core SAVVY principles and demonstrate the ability to tailor the implementation to match cultural values of the community? This inference procedure examines both the process (System Effectiveness Study) and the outcomes (preliminary Efficacy Study). The research team will follow a series of analytic steps to create meaning out of the relatively large amount of collected data, incorporating both the quantitative and qualitative components in a dynamic and interactive manner. We will look first at the results interventionists' ability to provide Savvy faithfully and in a manner congruent with local values: What conclusions or trends do fidelity monitoring, caregiver surveys, and interviews with all parties yield? Next we examine the impact of Savvy on participating caregivers to further establish the effectiveness of the system. If caregiver outcomes improve, this will provide a demonstration that system-trained interventionists can faithfully deliver Savvy in such a manner that its mechanism of action can have an expected effect on caregiver participants. If the outcomes do not support the effectiveness of this new system on either or both questions, we have the data to inform further system development work. The outcome of this process will be a finalized interventionist training system, one informed by a contextual understanding of the effects of the system and ready for a next step, a Stage III or IV intervention trial.

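### Improved caregiver outcomes are allowed to count as a demonstration of faithful delivery, although a gain over waiting, or a pooled before-after gain, does not show fidelity

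*Combined protocol and SAP*

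**What the plan says.** Section 5 (Study Design) makes fidelity the main object of the field trial: "The Aim 3 test will principally assess the effectiveness of the system in training interventionists who maintain fidelity to Savvy core principles". Section 10 (Plans for analysis) opens its synthesis with the same question: "Can the system train interventionists to maintain fidelity to core SAVVY principles", joined to the ability to tailor delivery to local culture.

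The synthesis has two steps. The first looks at direct evidence and asks: "What conclusions or trends do fidelity monitoring, caregiver surveys, and interviews with all parties yield". The second turns to caregiver outcomes: "Next we examine the impact of Savvy on participating caregivers to further establish the effectiveness of the system". The statement at issue follows: "If caregiver outcomes improve, this will provide a demonstration that system-trained interventionists can faithfully deliver Savvy". The sentence goes on to say that delivery would be such that the program's mechanism can have its expected effect. For unsupportive results ("If the outcomes do not support the effectiveness of this new system on either or both questions") the plan says only that the data will inform further development.

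The direct fidelity evidence is a caregiver survey that rates the interventionist and asks caregivers to "verify that certain key elements of the program were covered" (Field Methods), plus interviews. Setting and location says the same post-program survey is used in phase 3.

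The outcome evidence in Section 10 takes two main forms. One is the randomised comparison of immediate and waitlist groups, "using the first 2 time points (0m-2m) to test for differences between the 2 groups' changes post intervention". The other is a paired t-test that pools the before-after changes of both groups around their own Savvy program.

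**The concern.** The statement treats a benefit result as a fidelity result. Every program in the trial is led by system-trained interventionists, and the randomised alternative is waiting. There is no attention group and no concurrent arm led by interventionists trained in person. The contrast therefore estimates the effect of the class as delivered, including peer contact, attention and local adaptations. Whether an adaptation kept the core principles is part of the question being asked, and outcome scores cannot settle it.

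*Improve* is also undefined. The pooled paired test has no control, so a gain there could satisfy the sentence without any randomised difference.

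The fidelity strand has no cut-off in the text (Field Methods describes a look for notable problems), and there is no rule for the case where the two strands disagree. At stake is the conclusion that Section 10 would carry forward: that the training system works as intended and is ready for a Stage III or IV trial.

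**Working it through.** The plan gives no power, effect size, SD, correlation, dropout or fidelity threshold, so there is no figure of its own to reproduce. The point is mainly one of logic; the arithmetic only shows scale.

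**Logic**

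| Delivery | Outcomes improve | What the statement concludes | What the data support |
|---|---|---|---|
| Faithful | Yes | Faithful | Benefit of the class as delivered; fidelity only if the fidelity data show it |
| Unfaithful but supportive | Yes | Faithful | Benefit of the class as delivered; not shown to be Savvy |
| Faithful | No | Nothing stated about fidelity | Fidelity, if the fidelity data show it |
| Unfaithful | No | Nothing stated about fidelity | Neither |

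The second row is the error that the plan's wording permits.

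**Inputs for the illustration**
- Caregivers: 6 sponsors × 20 = 120 (Section 4, Aim 3). Equal allocation is assumed, giving 120/2 = 60 per arm.
- Significance level 5% (Section 10); two-sided is assumed.
- Assumed: SD = 1; non-specific effect of an unfaithful but supportive class over waiting d = 0.3 to 0.5 SD; baseline to follow-up correlation r = 0.6; no dropout; no clustering.

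**Chance that one outcome is significant in the favourable direction** = Φ(d/SE − 1.96)

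| Analysis | SE formula | SE | d = 0.3 | d = 0.5 |
|---|---|---|---|---|
| Follow-up only, unadjusted | √(2/60) | 0.183 | Φ(−0.32) = 0.38 | Φ(0.78) = 0.78 |
| Change score, r = 0.6 | √(2/60 × 2(1 − 0.6)) | 0.163 | Φ(−0.12) = 0.45 | Φ(1.10) = 0.86 |
| Baseline-adjusted, r = 0.6 | √(2/60 × (1 − 0.36)) | 0.146 | Φ(0.09) = 0.54 | Φ(1.46) = 0.93 |

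The change-score row is closest to the primary comparison in Section 10. Covariance adjustment appears there only conditionally, if the groups differ just before the intervention. With r below 0.5 the change-score figures would fall below the unadjusted ones. With an assumed 20% dropout (48 per arm) the unadjusted figures become 0.31 and 0.69.

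**How much a significant gain says about fidelity.** Suppose faithful delivery is worth 0.5 SD (unadjusted chance of significance 0.782). The likelihood ratio for faithful against unfaithful delivery is 0.782 divided by the same chance under unfaithful delivery:
- no non-specific effect: 0.782/0.025 = 31
- 0.2 SD: 0.782/0.194 = 4.0
- 0.3 SD: 0.782/0.376 = 2.1
- 0.5 SD: 0.782/0.782 = 1.0

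The outcome result is strong evidence of fidelity only if an unfaithful class does nothing for caregivers compared with waiting. The design cannot check that condition.

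**The case against.** The strongest reply is that Section 10 does not rest fidelity on outcomes alone. Direct fidelity evidence comes first, outcomes are brought in as further support, and the whole is a mixed-methods synthesis with no p-value trigger. The project is also an early-stage one with preliminary efficacy aims. This stands as far as it goes: a wrong answer requires outcomes to override or stand in for the fidelity evidence, which the plan does not prescribe. But it does not prevent this either. The sentence is not conditional on favourable fidelity data, and its closing reference to the mechanism of action does not help, because the mechanism is not isolated from group support.

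Waiting is not the only reference. Field Methods describes comparing caregivers' knowledgeability and competence responses with those from programs led by in-person-trained interventionists. That comparison is non-concurrent, limited to those responses, and set in text on the formative evaluation. It is a weak reference but should be acknowledged.

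A reader might also infer that a missed outcome test would be counted as a failure of fidelity. The documents do not support that as a rule. For unsupportive results they speak of either or both questions, which allows the two to come out differently, and promise only further development work.

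Finally, the percentages are ordinary power values under assumed effects. They say nothing about how likely unfaithful delivery is.

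**Conclusion.** The point holds in the positive direction only. Section 10 lets improved outcomes count as a demonstration of faithful delivery, without tying improvement to the randomised contrast and without a rule for discordant results. Neither a gain over waiting nor the pooled before-after gain shows fidelity, so the central question could be answered yes on evidence that does not bear on it.

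For scale, an unfaithful but supportive class would be significant on one outcome about 38 to 54% of the time at 0.3 SD and 78 to 93% at 0.5 SD. These ranges rest on 60 per arm, the assumed effects, r = 0.6 where used, and no dropout or clustering. The logical conclusion depends on none of these figures; it needs only that an unfaithful class could help caregivers.

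It would go too far to say that outcomes are the sole basis for the fidelity conclusion, or that the plan would declare fidelity failed after a null outcome.

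**What to change.** In Section 10:

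1. Delete the statement that improvement demonstrates faithful delivery.
2. Base the fidelity conclusion on the fidelity survey and the interviews, against a criterion fixed before outcome data are seen. The survey's appendix is not in the text available here, so the criterion has to be set by the study team from its actual scoring.
3. Base the caregiver-benefit conclusion on the randomised immediate-versus-waitlist contrast, and label the pooled paired test as supportive.
4. State how the four combinations will be read: fidelity and benefit; fidelity without benefit; benefit without fidelity, read as a benefit of the class as delivered and not shown to be Savvy; and neither.
5. The strands may still be integrated descriptively, for example in an exploratory table of program-level fidelity score against program-level outcome change.

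This needs no new data collection. The cost is slightly more wording, one descriptive table if wanted, and a narrower stated conclusion.

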## **11. Training of study team**

The Project Director will oversee the training of all staff members on the team, ensuring that they have completed or renewed CITI trainings at appropriate intervals. She will also develop standard operating procedures (SOPs) to ensure that study staff maintains the highest standards of data protection and management. For any staff members who will have participant contact, the project director will provide

opportunity for them to practice interview technique prior to any contacts with human subjects. They will also be monitored regularly to ensure best practices are maintained for data collection. The SOPs will be updated regularly in order to reflect current practices by study staff.

## **12. Plans for monitoring the study for safety**

The project PI ([name]) and the project Co-PI ([name]) will be responsible for ensuring participants' safety in this minimal risk, single-site study. Per concurrence of the NIA Program Officer, because this study is being conducted at a single site, involves fewer than 200 subjects, and is not a clinical trial it does not require a Data Safety and Monitoring Board. Instead, the Associate Dean for Research at the Nell Hodgson Woodruff School of Nursing ([name]) has agreed to serve as the Safety Officer for the project.

### **Frequency of Data and Safety Monitoring**

The PI will be informed of any deaths as soon as they occur and will notify the NIA Program Officer and the Safety Officer (SO) within 24 hours of notification; the PI will also inform the Emory IRB of any such events within the time frame specified by the IRB. Beginning with the initiation of study phase 2 activities, the PI ([name]) will be responsible for providing quarterly summary reports of SAEs to the NIA Program Officer and the SO. Beginning with the initiation of phase 2 activities, safety reports will be sent to the SO twice a year and will include a detailed analysis of study progress, data and safety issues. Such reports will be developed by the co-PIs but reviewed by key study personnel and, as appropriate, study consultants and advisors.

### **Content of Data and Safety Monitoring Report**

The study PI ([name]) will provide semi-annual data safety and monitoring reports to the NIA Program Officer and the SO. Each report will update the previous report. Each report will summarize:

- Overall study status
- Study participant characteristics
- Study recruitment and retention statistics
- Data completeness
- Summary statistics on caregiver and care recipient outcome measures
- Deployment of the risk protocol based on observations or scale scores
- Unanticipated Serious Adverse Events, including Deaths.

#### *DSMB Membership and Affiliation*

The Safety Officer for this study will be:

[name], RN, FAAN  
Associate Dean for Research  
Nell Hodgson Woodruff School of Nursing, Emory University

[name] is a well-established researcher, currently supported by an RO1 and a P30 grant from NINR, with an extensive track record of completed externally-supported research. As Associate Dean for Research within the School of Nursing, she heads the Office of Nursing Research; as such, she has at her disposal a variety of methodological and statistical experts, should she need them to fulfill her responsibilities as Safety Officer.

The SO will:

- Review the research protocol, informed consent documents and plans for data safety and monitoring;
- Recommend subject recruitment be initiated after receipt of a satisfactory protocol;
- Evaluate the progress of the trial, including periodic assessments of data quality and timeliness, recruitment, accrual and retention, participant risk versus benefit, performance of the trial sites, and other factors that can affect study outcome;
- Consider factors external to the study when relevant information becomes available, such as scientific or therapeutic developments that may have an impact on the safety of the participants or the ethics of the trial;
- Review study performance, make recommendations and assist in the resolution of problems reported by the Principal Investigator;
- Protect the safety of the study participants;
- Report to NIA on the safety and progress of the trial;
- Make recommendations to the NIA and the Principal Investigator concerning continuation, termination or other modifications of the trial based on the observed beneficial or adverse effects of the treatment under study;
- If appropriate, review interim analyses in accordance with stopping rules, which are clearly defined in advance of data analysis and have the approval of the SO;
- Ensure the confidentiality of the study data and the results of monitoring; and,
- Assist the NIA by commenting on any problems with study conduct, enrollment, sample size, and/or data collection.

### **13. Confidentiality**

Participant confidentiality and privacy is strictly held in trust by the participating investigators, their staff, and the sponsor. The study documentation, data, videotaped interviews, and all other information generated will be held in strict confidence. No information concerning the study or the data will be released to any unauthorized third party without prior written approval of the sponsor.

All research activities will be conducted in as private a setting as possible.

The study monitor, other authorized representatives of the sponsor, representatives of the Institutional Review Board (IRB), regulatory agencies may inspect all documents and records required to be maintained by the investigator for the participants in this study. The clinical study site will permit access to such records.

Study participant research data, which is for purposes of statistical analysis and scientific reporting, will be directly entered into and stored in the password-protected excel database. Individual participants and their research data will be identified by a unique study identification number. All information collected during the study will be secured and password protected. At the end of the study, all study databases will be de-identified and archived at the Emory School of Nursing.

The study participant's contact information will be securely stored in a separate password protected excel database for internal use during the study. This document will provide a linkage between name of participant

and a unique study identification number. At the end of the study, this linkage document all paper records will continue to be kept in a secure location for as long a period as dictated by the reviewing IRB, Institutional policies, or sponsor requirements.

